### 7.1 Evaluation Criteria

## 7.1.1 Safety Endpoints

All patients receiving any protocol treatment will be evaluated for safety. Safety assessments will include:

- i. Incidence and severity of adverse events.
- ii. Incidence of dose limiting toxicities (DLT) defined in section 7.4.

### 7.1.2 Immunologic Endpoints

All eligible patients for which the required follow-up tissue and blood samples are obtained will be evaluated for the difference in pre and post-CRT samples; difference in pre and during CRT samples; and difference in during CRT and post-CRT samples:

- i. ratio of CD8+ T cells to Tregs
- ii. HPV E2
- iii. E7 specific CD8+ T cells
- iv. regulatory FoxP3+ T cells (Tregs)

#### 7.1.3 Efficacy Endpoints

All eligible patients for which a PET/CT imaging is obtained 12 weeks after CRT will be evaluated for complete metabolic response.

All eligible patients with follow-up information on disease status will be evaluated for the occurrence of distant metastasis as the first site of recurrence, progression-free survival and overall survival.

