#### 2.0 TRIAL DESIGN

## 2.1 Trial Design

This is a randomized, Phase II, open-label multi-center study in which 88 eligible subjects with locally advanced cervical cancer will be treated with standard chemoradiation treatment (CRT) plus the PD-L1 monoclonal antibody pembrolizumab. The primary objectives in the study will be to estimate the safety and immune response to pembrolizumab given either sequentially or concurrently with CRT. Secondary objectives will evaluate the metabolic response and rates of distant metastases following treatment with pembrolizumab given sequentially or concurrently with CRT. The study design also affords the opportunity to characterize the effect of treatment on immune response pathways by estimating the effects of treatment on specific immune markers.

At baseline, subjects will undergo a full medical history and physical examination, vital signs, performance status, and general laboratory evaluations. Baseline imaging assessments will include PET/CT and MRI (MRI is required, unless there are contraindications or at the discretion of the investigator). Eligible subjects (n=88) will be randomized 1:1 to two treatment sequences to receive pembrolizumab after completion of CRT (Arm 1) or to receive pembrolizumab concurrent to CRT (Arm 2). Subjects in both arms will receive identical regimen, as follows:

- Chemotherapy: Weekly Cisplatin (40 mg/m^2) for 5 or 6 weeks
- Radiation: Standard dose IMRT with 4-6 fractions of high-dose-rate (HDR) brachytherapy using standard doses and methods
- Pembrolizumab: 200 mg, 3 cycles (every 21 days)

Subjects will be evaluated for safety by monitoring for adverse events. All subjects will have a PET/CT approximately 12 weeks following completion of all CRT to evaluate for response. Tumor and blood samples will be collected at baseline, during CRT and post-treatment for analysis of immune response markers. All subjects will be followed for disease-free survival and overall survival for up to 5 years.

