#### 3.2 Secondary Objectives

- To estimate rates of complete metabolic response on PET/CT imaging obtained 12 weeks after CRT.
- (2) To estimate rates of distant metastasis as the first site of recurrence for patients.
- (3) To estimate the influence of concurrent and consolidative MK-3475 on levels of plasminogen activator inhibitor-1 (PAI-1), a marker of immunosuppressive TGF-B.
- (4) To estimate the influence of concurrent and consolidative MK-3475 on levels of IDO, an enzyme that depletes tryptophan, which is essential for T-cell function.
- (5) To estimate the influence of concurrent and consolidative MK-3475 on levels of MHC class I (CD8+ T cell ligand) and MICA (NK ligand), as measured by MHC.
- (6) To estimate the progression free survival (PFS) in subjects with locally advanced cervical cancer treated with sequential and concurrent administration of pembrolizumab in relation to CRT.
- (7) To estimate the overall survival (OS) in subjects with locally advanced cervical cancer treated with sequential and concurrent administration of pembrolizumab in relation to CRT.

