## 5.7.1 Duration of Treatment

Subjects will continue to receive study treatment (defined as chemoradiation and pembrolizumab) until:

- Subject has completed all study treatments
- Disease progression
- Unacceptable adverse event(s)
- Subject withdraws consent for further treatment
- · Female subject has a confirmed positive serum pregnancy test
- Subject receives a non-study treatment (not protocol-specified) for their cancer
- Subject non-compliance
- General or specific changes in the subject's condition render the subject unacceptable for further treatment in the judgment of the investigator

If any of the above events occurs, the subject will be considered off treatment and in follow-up. Subjects will be followed for 5 years for PFS and OS, or until the trial is terminated per Section 5.7.4.

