## 6.0 TRIAL FLOW CHART

## 6.1 Study Flow Chart

# 6.1.1 Arm 1

Trial Period:	Pre- Study	Treatment		Post-treatment		Survival
Visit:	Screening	CRT	Pembro	EOT visit 	Imaging	Follow-
Scheduling Interval:	-42d-1d	W1-W8	W9-W15	35 ± 5d	12w ± 10d post-CRT	Up 
Administrative Procedures						
Informed Consent/ IE	Х					
Demographics/Medical History	Х					
Concomitant Medication Review	Х					
Disease Status						Х
Survival Status						Х
Study Treatments						
Cisplatin		Х				
Radiation		Х				
MK-3475 administration			x 			
Specimen Collection						
Tissue Collection 	Х	x 			Х	
Research Blood Collection	Х	X 			Х	
Clinical Procedures/ Laboratory Assessments						
Pregnancy Test (Urine or Serum) 	х					
Review Adverse Events	Х	Х	Х	Х		

<sup>1 All subjects should be followed for 5 years following treatment to monitor disease status and overall survival. There are no per protocol assessments, all subjects should be monitored according to the standard of care of the treating physicians.

<sup>2 Each subject should return to the clinic for a visit 30-40 days following the last study treatment (of either pembrolizumab or chemoradiation) for assessment of adverse events

<sup>3 Pembrolizumab treatment should be scheduled for every 21 days ( $\pm$  3 days) starting on Week 9.

<sup>4 Fresh tissue biopsies are required. If archival tissue is available these may also be submitted to supplement fresh tissue collected at baseline.

<sup>5 Tissue and blood specimen collected during CRT interval should be obtained at  $5 \pm 2$  weeks

<sup>6 Women of childbearing potential must have a negative pregnancy test within 72 hours of first dose of study treatment.

Trial Period:	Pre- Study	Treat	tment	Post-tre	Survival		
Visit:	Screening	CRT	Pembro	EOT visit 	Imaging	Follow-	
Scheduling Interval:	-42d-1d	W1-W8	W9-W15	35 ± 5d	12w ± 10d post-CRT	Up 	
Physical Examination/ECOG	X7	X 	X 	х	X 		
Vital Signs	Х	Х	Х	Х			
PT/INR and aPTT 	Х						
CBC with Differential 	Х	x 	X 	Х			
Serum Chemistry Panel 	Х	X 	X 	Х			
Thyroid panel 	Х		X 	Х			
	Tumor Imaging/Disease Assessments						

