### 6.3.4.1 Tumor Imaging and Assessment of Disease

Baseline imaging should be obtained within 6 weeks of the start of treatment and should include MRI and PET/CT. A pelvic MRI is required only at the Pre-Study Assessments unless there are contraindications or at the discretion of investigator.

PET/CT should be inclusive of the skull base to the thigh area ("eyes to thighs") and should be performed during the Pre-Study Assessments for initial staging. PET/CT should be repeated at 12 weeks ± 10 days after completion of CRT for evaluation of disease.

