#### 7.5 Analyses

The study is designed with sufficient power to assess pre/post change in immune measures with an ES of .45 within each arm and not to detect a predetermined difference in the changes overtime between the two arms. However, data from the study will be used to estimate; the magnitude of the difference in pre/post change for all parameters of interest between the two arms; as well as progression—free and overall survival. With 44 eligible patients per arm we have 67%, 75% and 87% power to detect an ES of 0.45, 0.5 and 0.6, respectively, for continuous immune parameters (normality assumed) with a 10% level t-test. With 44 patients the width of a 90% CI (exact Clopper-Pearson) around the complete metabolic response at 3 months of 70% and the distant metastases rate at 3 years of 20% are (57%, 81%) and (10%, 33%), respectively. Thus, any estimated rate outside of these bounds would be considered promising. For each arm, progression free survival (PFS) and overall survival will be estimated by the product-limit method of Kaplan and Meier along with 90% confidence bands. In patients with complete metabolic response at 3 months, 3-year PFS is 78% (Schwartz et al, 2007). This result will be used to guide interpretation of results on PFS from this study.

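### Complete metabolic response is counted only in patients who have the 12-week PET/CT, with no rule that counts failure before the scan as non-response

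*Combined protocol and SAP*

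**What the plan says.** CMR is the first secondary objective in Section 3.2: "To estimate rates of complete metabolic response on PET/CT imaging obtained 12 weeks after CRT". Section 7.1.3 defines who is analysed: "All eligible patients for which a PET/CT imaging is obtained 12 weeks after CRT will be evaluated for complete metabolic response".

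The scan is planned for everyone. Section 2.1 states: "All subjects will have a PET/CT approximately 12 weeks following completion of all CRT to evaluate for response". Section 6.3.4.1 gives the window: "PET/CT should be repeated at 12 weeks ± 10 days after completion of CRT for evaluation of disease". Both flow charts in Section 6.1 show imaging as a post-treatment visit, and none of these places makes an exception for progression.

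Section 7.5 gives the precision in a sentence that begins "With 44 patients the width of a 90% CI (exact Clopper-Pearson) around the complete metabolic response at 3 months of 70" per cent. It reports bounds of 57% and 81% and says that an estimated rate outside them would be regarded as promising.

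No section says how to count a patient who dies, progresses, begins other anticancer therapy or misses the scan for another reason before the 12-week time point. By contrast, Section 7.1.1 evaluates safety in every patient who receives any protocol treatment. An all-treated set therefore exists in the plan but is not used for CMR.

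**The concern.** Having the scan is a condition for entering the analysis, and it is met well after treatment starts. Section 5.3.3.3 allows up to 8 weeks for all radiation, so the scan can fall at about week 8 + 12 = 20, plus the window. Several things can prevent it in that time. Patients who die cannot be scanned. Under Section 5.7.2, patients who withdraw consent are not followed further. Patients who progress or receive other therapy may be managed elsewhere or imaged off schedule, and an earlier scan showing recurrence does not fit the wording of 7.1.3. For a patient who never completes CRT, the 12 weeks has no defined starting date.

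Some of these patients are failures by any reading of the endpoint. Under 7.1.3 they leave the denominator when they should stay in it as non-responders. The result then estimates response among patients who reached the scan, which is not the same as response among patients treated. The distortion can also differ by arm if the two schedules differ in early failure.

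**Working it through.** **Inputs.** From Section 7.5: CMR 70%, 44 patients per arm, 90% exact Clopper-Pearson interval, stated bounds 57% and 81%. From Section 7.2: 10% allowance for ineligibility and drop-out, maximum accrual 98. The number m of unscanned patients per arm is not in the documents; I assume 2 to 8. The fraction q of unscanned patients who would have been in CMR is also not given.

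**1. The plan's interval.** The limits are the 5th percentile of Beta(x, n − x + 1) and the 95th percentile of Beta(x + 1, n − x). With x = 0.70 × 44 = 30.8 and n = 44 they are 56.7% and 81.2%, which round to the stated figures. The nearest whole count, 31/44 = 70.5%, gives 57.2% and 81.6%. The stated interval reproduces.

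**2. Effect of excluding unscanned failures.** Let C be the number of true CMRs among N eligible treated patients. The rate under 7.1.3 is (C − q·m)/(N − m), against C/N with everyone counted. For patients who failed before the scan, q = 0 and the rate is C/(N − m), which exceeds C/N for any m above zero. With C = 31 and N = 44:

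| m excluded | Rate under 7.1.3 | Excess over 70.5% |
|---|---|---|
| 2 | 31/42 = 73.8% | 3.4 points |
| 4 | 31/40 = 77.5% | 7.0 points |
| 6 | 31/38 = 81.6% | 11.1 points |
| 8 | 31/36 = 86.1% | 15.7 points |

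Six exclusions bring the estimate to about the upper bound. Starting from 30/44 = 68.2%, it takes seven: 30/37 = 81.1%.

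**3. Sensitivity to who is missing.** Keep C = 31, N = 44 and m = 4:

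- q = 0: 31/40 = 77.5%, bias +7.0 points
- q = 0.35: (31 − 1.4)/40 = 74.0%, bias +3.5 points
- q = 0.70: (31 − 2.8)/40 = 70.5%, bias about 0
- q = 0.90: (31 − 3.6)/40 = 68.5%, bias −2.0 points

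The direction is certain only for patients who failed before the scan. For scans missing for unrelated reasons there may be no bias.

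**4. The 10% allowance.** 88/0.90 = 97.8, rounded up to 98. The allowance is used up in going from 88 to 98 accrued. It is not an expected number of missing scans among the 44.

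**The case against.** A reader might infer that patients who progress have no scheduled scan, because Section 5.7.1 says "If any of the above events occurs, the subject will be considered off treatment and in follow-up" and a flow-chart footnote says "There are no per protocol assessments, all subjects should be monitored according to the standard of care of the treating physicians". The documents do not support that. The footnote belongs to the survival follow-up column, and imaging is a separate visit. The list in 5.7.1 also includes "Subject has completed all study treatments", so the same status applies to completers, who are clearly meant to be scanned. What stands is narrower: scheduling a scan for all does not produce one from a patient who has died or withdrawn, and the wording of 7.1.3 itself allows for scans that are not obtained.

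Toxicity is also a weak route to a missing scan. Sections 5.3.2.1 and 5.3.2.4 let patients continue on study without further pembrolizumab or without cisplatin.

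The figure of 44 can fairly be read as the evaluable number after drop-out, so Section 7.5 does not plainly contradict 7.1.3. The estimate is conditional on being scanned either way. If 44 counts eligible patients, the bounds assume that all are scanned. If it counts scanned patients, the failures have already been removed.

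Six exclusions would need 6 of 13 non-responders (46%) to be unscanned. Even then 31/38 = 81.6% matches the upper limit for 31/44, so whether it crosses the bound turns on rounding.

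Finally, CMR is secondary, Section 7.0 disclaims definitive comparison of the arms, and early failures still appear in PFS, OS and first-site distant metastasis. This limits the consequence but does not correct the CMR rate.

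**Conclusion.** The point holds as a conditional risk. Section 7.1.3 makes the scan an entry condition, and no rule keeps patients who failed earlier in the denominator. Following the text therefore drops any such patient who was not scanned and raises the reported rate.

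The excess is 3.4 to 11.1 points for 2 to 6 unscanned failures per arm, from a true 31/44. That range rests on assumed counts and on all of those patients being non-responders. It would be wrong to conclude that the rate is certain to be inflated, that about 10% of scans will be missing, or that the ranking of the arms will be distorted: the documents give no early-failure or missing-scan rate in either arm. The primary objectives are unaffected. The change is worth making because 7.5 attaches an interpretation to the CMR rate and the correction is cheap.

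**What to change.** In 7.1.3 and 7.5:

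- Use all eligible patients who started treatment, by randomised arm, as the CMR denominator. This fits Section 5.7.3, which replaces patients who leave before any treatment.
- Count death, progression or new anticancer therapy before the scan as not CMR.
- Report the number of scans missing for other reasons by arm, and count them as not CMR in the main estimate.
- Give the scanned-only rate as a sensitivity analysis.
- State from what date the 12 weeks is timed for patients who do not complete CRT, and confirm that patients who stop early keep the scan.

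This needs wording only and no new data. The downside is a slightly lower, more conservative rate. The third rule is pessimistic if scans are missing for unrelated reasons: with 28 CMR among 40 scanned (70.0%) and 4 missing, the main estimate would be 28/44 = 63.6%. Reporting the scanned-only rate beside it lets the reader see that difference.

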## 5.7.2 Discontinuation/Withdrawal from Study

Subjects may withdraw or be discontinued from the study at any time for any of the following reasons:

- Subject decides to withdraw from the study
- Subject is unable or unwilling to complete the follow-up procedures
- The subject is lost to follow-up
- Death

The primary reason for discontinuation or withdrawal should be entered into OnCore. All subjects that discontinue or withdraw from the study will continue to receive standard of care treatment. Subjects who have withdrawn consent for the study will not be followed for any reason.

A subject's participation is considered completed when the subject has completed the 5 year followup interval.

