#### 6.3.5.4 Survival Follow-up

Following completion of treatment, subjects should be followed for 5 years to monitor disease and survival. No assessments are specified for this interval, but it is recommended that surveillance follow NCCN guidelines. Subjects should be contacted by telephone annually to assess for disease and survival status until death, withdrawal of consent, or the end of the study, whichever occurs first.

Protocol/Amendment No.: UVA-LACC-PD201, Version 4.0, 06 March 2018

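### Section 7.1.3 limits the PFS and OS analyses to patients with disease-status follow-up; read literally, this drops known early deaths and biases survival upward

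*Combined protocol and SAP*

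**What the plan says.** Section 7.1.3 (Efficacy Endpoints) reads "All eligible patients with follow-up information on disease status will be evaluated for the occurrence of distant metastasis as the first site of recurrence", and the same sentence goes on to "progression-free survival and overall survival". No other section names a population for these three endpoints.

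Section 7.5 (Analyses) gives the estimator: "For each arm, progression free survival (PFS) and overall survival will be estimated by the product-limit method of Kaplan and Meier", with 90% confidence bands. It states no analysis set, time origin, event definition or censoring rule for either endpoint.

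On follow-up, Section 5.7.1 says "Subjects will be followed for 5 years for PFS and OS". Section 6.3.5.4 says "Following completion of treatment, subjects should be followed for 5 years to monitor disease and survival" and also "Subjects should be contacted by telephone annually to assess for disease and survival status until death". The flow charts in Sections 6.1.1 and 6.1.2 carry disease status and survival status as two separate rows, both marked only in the survival follow-up column. The PET/CT 12 weeks after CRT has its own column and is described in Section 6.3.4.1.

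The safety population in Section 7.1.1 is everyone who receives any protocol treatment, with no such condition.

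**The concern.** A survival analysis should not admit patients according to what was observed after baseline. OS needs only vital status, and the protocol records that separately from disease status. A patient can therefore have a known date of death and no disease-status record. If Section 7.1.3 is followed to the letter, she leaves both the OS and the PFS analysis.

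The patients at risk of this are those who die during CRT or pembrolizumab, or shortly afterwards, before any disease assessment. Many of these deaths would be known to the trial. Section 6.4.4.1 requires deaths from causes other than progression to be reported from the start of treatment to 30 days after the last dose (or to new anticancer therapy, if earlier), and Section 5.7.2 lists death among the off-study reasons, the primary one of which is recorded. The analysis would then omit events that the trial had captured. Kaplan-Meier needs no such filter, since short follow-up is handled by censoring.

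Section 1.0 names historical data as part of the control, and Section 7.5 will read PFS against an outside 3-year figure of 78%. An upward shift in the whole-arm curve would make that reading more favourable than it should be.

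**Working it through.** **Inputs.** 44 patients per arm (Sections 7.2 and 7.5); 5-year OS of 66% after CRT (Section 4.1), used only as an illustration; distant-metastasis rate of 20% at 3 years (Section 7.5). The number of patients excluded, k, is not in the documents and is assumed to be 1 to 4 per arm.

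**1. The plan's own figures.** Section 7.5 gives exact 90% Clopper-Pearson intervals for n = 44. The lower limit is the 5% quantile of Beta(x, n − x + 1) and the upper limit the 95% quantile of Beta(x + 1, n − x).
- Distant metastasis at 20%: x = 8.8 gives (10.8%, 32.5%) and x = 9 gives (11.1%, 33.0%). The plan states (10%, 33%), which agrees within about 1 point.
- Metabolic response at 70%: x = 30.8 gives (56.7%, 81.2%). The plan states (57%, 81%).

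These intervals put all 44 patients of an arm in the denominator. The precision statement does not allow for the filter in Section 7.1.3.

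**2. The exposed window.** Sections 5.3.2.3 and 5.3.3.3 allow up to 8 weeks for radiation. The PET/CT follows 12 weeks (± 10 days) after CRT. If that scan is the first disease-status record, the window runs to about 8 + 12 = 20 weeks from the start of CRT. It covers all of CRT and, in Arm 1, pembrolizumab in weeks 9 to 15. If only the survival follow-up column counts, the window is longer.

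**3. Early deaths left out.** Take 15 deaths among 44 by 5 years and no earlier censoring. Kaplan-Meier OS is then 29/44 = 65.9%. With k early deaths removed it is 29/(44 − k).

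| k excluded (assumed) | OS estimate | Rise in points |
|---|---|---|
| 0 | 29/44 = 65.9% | – |
| 1 | 29/43 = 67.4% | 1.5 |
| 2 | 29/42 = 69.0% | 3.1 |
| 3 | 29/41 = 70.7% | 4.8 |
| 4 | 29/40 = 72.5% | 6.6 |

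The same arithmetic near the 78% PFS figure: 34/44 = 77.3% becomes 34/43 = 79.1% for k = 1 and 34/40 = 85.0% for k = 4.

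**4. Patients lost with no follow-up time.** A patient censored at day 0 is in no later risk set, so censoring her and excluding her give the same curve. With 15 deaths and 4 of the other patients lost at day 0, OS is 25/40 = 62.5% either way. Exclusion adds no bias of its own here.

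**5. Distant metastasis as first recurrence.** Start from 9/44 = 20.5%. Excluding four patients gives 9/40 = 22.5% if none of them had distant metastasis and 5/40 = 12.5% if all four did. The direction is not fixed.

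**The case against.** The strongest reply is that dropping early deaths is a reading of loose wording and not a stated rule. No section says that a death fails to count as follow-up. Section 5.7.1 moves every patient who stops treatment into 5 years of follow-up, Section 5.7.3 starts follow-up on that date, Section 6.3.5.4 treats death as the end of contact, and Section 7.5 names Kaplan-Meier without repeating the filter. A sensible analyst might well keep the early deaths.

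That is fair as to intent. But the condition concerns disease status, which the flow charts separate from survival status, and Section 7.1.3 is the only text that sets the population. In an open-label trial the choice between the two readings should not be left until outcomes are known.

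The reply on size also stands in part. The window is short, examinations take place during treatment, and k is assumed; k = 4 would mean 9% of an arm dying before any disease-status record. A rise of 1.5 to 3.1 points is small beside a 90% interval of roughly ± 12 points (57% to 81% around 70%). The endpoints are secondary, Section 7.0 disclaims definitive comparisons between arms, and treatment-related deaths are still counted in the safety analysis.

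Three stronger readings are tempting and are not supported:
- That patients lost before any contact also inflate survival. Step 4 shows that their exclusion changes nothing. If loss is related to prognosis there may be bias, but keeping them with zero follow-up would not remove it.
- That the distant-metastasis rate is biased in a known direction. Step 5 shows that it is not.
- That Section 5.7.2, by listing "Subject is unable or unwilling to complete the follow-up procedures" as a reason to leave the study, systematically removes the sickest patients from survival follow-up. Section 6.3.5.4 specifies no assessments in that period, only an annual call, and Section 5.7.2 bars further follow-up only after withdrawal of consent.

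**Conclusion.** The point holds in a limited form. Section 7.1.3 makes entry to the PFS and OS analyses depend on post-baseline disease-status information, and nothing else in the plan overrides it. Applied literally, it omits known deaths and biases survival upward in the arm where they occur. If early deaths differ between schedules, the descriptive comparison of arms shifts too.

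For 1 to 4 excluded deaths in 44 and a 5-year OS of about 66%, the rise is about 1.5 to 6.6 points. This assumes that every excluded patient is an early death and that there is no other censoring before 5 years. The documents give no count, and it is probably at the low end.

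A reader might infer that the comparison with the 78% PFS figure is certain to be inflated. That figure belongs to patients with complete metabolic response at 3 months. Within that subgroup nobody who died before the scan could be included, so the filter is irrelevant there; it matters if the whole-arm PFS is set beside 78%.

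No primary objective and no stopping rule depends on these endpoints. The wording should still be corrected, because the correction is nearly free and removes a choice that could otherwise be made after the data are seen.

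**What to change.** In Section 7.1.3, replace the condition on disease-status information for PFS and OS with the following, and carry the definitions into Section 7.5:
- Population: all eligible randomised patients who start protocol treatment, by arm. This fits Section 5.7.3, under which patients who leave before any treatment are not accruals and are replaced. A set of all randomised patients would conflict with that rule unless it too were changed.
- Time origin: named, for example randomisation. Since untreated patients are replaced, the interval from randomisation to first treatment is free of deaths by construction, so start of treatment is an equally defensible choice. One should be stated.
- Events: death from any cause counts for both OS and PFS; progression also counts for PFS.
- Censoring: patients without disease-status follow-up are kept, and are censored at the last disease assessment for PFS or the last date known alive for OS.

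For distant metastasis as first site of recurrence, use the same patients and estimate a cumulative incidence, with death and other first recurrence as competing events. A simple proportion over the same denominator would count unassessed patients as free of metastasis.

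The cost is a few sentences. Deaths are already recorded through safety reporting, off-study reasons and survival status, so no new data are needed. The one downside is that the survival figures may be slightly less favourable.
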